### **13.4 Procedure for AE and SAE Reporting**

All AEs and SAEs must be documented in the participant's CRF. SAEs may also require immediate reporting by the site, as below:

Actions for SAEs:

1. Report immediately, within 24 hours of becoming aware of the event:
  - SAR – suspected adverse reaction.
  - Unexpected SAE.

- SUSAR – Suspected Unexpected Serious Adverse Reaction.
2. Documented in the CRF only (do not require immediate reporting):
- Expected SAE.

Unexpected SAEs, SUSARs and SARs will be reported to the C\*STEROID DMC, regulatory authorities and ethics committees, as required.

### **13.5 Data and Safety Monitoring**

A Safety Monitoring Committee (SMC) will review all serious adverse events. This committee will include a senior obstetrician and a senior neonatologist, as a minimum. The SMC will report to the Trial Steering Committee (TSC). The TSC will report any safety issues to an independent Data Monitoring Committee (DMC).

The C\*STEROID DMC has established terms of reference and will include a senior obstetrician, a senior neonatologist and a biostatistician, as a minimum. The DMC will review trial safety, efficacy and conduct and report to the TSC.

### **13.6 Interim Analysis**

There are no planned interim analyses. The DMC will review adverse and serious adverse events and have the ability to recommend early termination if a clear and significant unfavourable benefit-to-risk profile is demonstrated.

## **14. CONFIDENTIALITY & DATA MANAGEMENT**

### **14.1 Confidentiality**

Participants will be assigned a study ID number and data will be recorded against this. Data will be entered onto hard copy CRFs and/or directly into an electronic eCRF database stored on secure servers. Access to the eCRF database will be controlled by unique user ID and password, with full electronic tracking log.

Completed hard copy CRFs and a copy of the signed consent form will be securely transmitted to the Auckland coordinating centre, including contact details with identifying information for the purpose of enabling longer term follow up. Electronic and hard copy data will be securely stored in the Liggins Institute, The University of Auckland for a minimum of 10 years (maternal) and for a minimum of 10 years after the age of majority (child). Study reports will contain only summary data. Identifiable data will not be reported or released to any third party.

We will utilise social media to raise awareness of the C\*STEROID Trial. This will allow participants to potentially identify themselves. The participant information sheet and consent form will include reference to this.

All investigators, clinicians and participants will remain blinded to treatment allocations throughout the study. If a participant is un-blinded due to an urgent clinical need to reveal the

study allocation the investigator is advised to limit the distribution of this information to other site staff or study personnel.

#### **14.2 Access to Data and Data Sharing**

The Trial Steering Committee will have access to the full dataset and oversee analysis, interpretation and reporting of results. The de-identified data that support the findings of this study will be made available upon request to researchers who provide a methodologically sound proposal and whose proposed use of the data has been approved by an independent review committee identified for this purpose following publication of the primary C\*STEROID Trial results.

#### **14.3 Data Management Plan**

Further detail regarding data management is documented in the Data Management Plan.

### **15. OUTCOME MEASURES**

#### **15.1 Primary Outcome**

We have selected co-primary outcomes to accurately assess benefit *and* harm. These are:

- **Co-primary outcome (neonatal benefit):** incidence of respiratory distress requiring >60 minutes\* of respiratory support. Includes mechanical and non-invasive ventilation where sum of both is >60 minutes (e.g. intermittent positive pressure via endotracheal tube, nasal continuous positive airway pressure, Hi- or Lo-flow oxygen/air mix or increased ambient oxygen delivered into an incubator). *\*>60 minutes selected to eliminate short-term support which may be subject to variation by clinician.*
- **Co-primary outcome (neonatal harm):** incidence of hypoglycaemia (blood glucose level <2.6 mmol/L) prior to primary hospital discharge.

We hypothesise that corticosteroid use will reduce neonatal respiratory distress without increasing neonatal hypoglycaemia and therefore have selected co-primary outcomes of a superiority endpoint for benefit and non-inferiority endpoint for harm. The efficacy of corticosteroids is based on the success of both co-primary endpoints; therefore, no multiplicity adjustment is necessary.

#### **15.2 Secondary Outcomes**

The following clinically relevant, reproducible and easily defined neonatal and maternal outcomes that reflect potential benefit and/or harm will be collected:

- NNU admission
- Duration of NNU stay
- Duration of neonatal hospital stay (to primary hospital discharge)

- Duration of neonatal respiratory support (sum of mechanical and non-invasive)
- Severe respiratory distress defined as any mechanical ventilation and/or need for surfactant therapy; moderate respiratory distress defined as respiratory support (sum of mechanical and non-invasive) for >24 hours
- Severe neonatal hypoglycaemia defined as blood glucose level <1.2 mmol/L
- Early onset infection and/or late onset infection as defined by ANZNN
- Maternal self-reported adverse effects of injections including gastrointestinal upset; insomnia; pain, bruising or infection at injection site;
- Maternal perinatal infectious morbidity requiring postpartum antibiotic therapy;
- Duration of maternal postnatal stay (to primary hospital discharge);
- Breastfeeding (exclusive and full) at six weeks postpartum, and
- Maternal wellbeing and psychological status measured at six weeks postpartum.

### 15.3 Childhood Outcomes

Assessment in childhood is beyond the scope of current funding cycles. However, plans to assess childhood benefits and harms is an important and unique feature of the trial. Trial consent will include a request to maintain contact with families for later invitation to follow-up studies, and for Australian sites, we will include an option to consent for later linkage to maternal and child health records and child educational records.

We anticipate C\*STEROID children will undergo a multi-dimensional assessment at 6-7 years of age co-ordinated through the Liggins Institute Follow-up Programme. This assessment has been designed to be portable for school or office use; completed within a typical school timetable block; and conducted and analysed using a tablet computer. Tests can be administered by trained assessors and do not require the presence of a paediatrician or psychologist. Parent surveys with high readability can be completed online or in hard copy. Using this method we will be able to assess accurately neurocognition (language, memory, executive function, sensory processing, motor function) health and wellbeing (emotion, behaviour, physical health, growth) and cardiometabolic function (body composition, musculoskeletal and vascular development).

## 16. STATISTICAL ANALYSES

Data will be analysed on an intention-to-treat basis. To account for the correlation of twins, we will use marginal logistic regression model via generalised estimating equations to assess the treatment effect on respiratory distress adjusting for randomisation variables and other confounders which may influence the outcome of interest including by indication for CS. Two sided-p-values less than 0.05 will be used to determine statistical significance and confidence intervals will be reported at a two-sided 95% level. Farrington-Manning score test will be used for assessing non-inferiority to compare hypoglycaemia rate between the two groups. Non-inferiority is established if the upper limit of the 90% confidence interval of the proportion difference between the two groups (steroid-placebo) is not greater than 10%. Descriptive summary statistics will be provided for continuous variables with mean, standard deviation, median, minimum and maximum and for categorical variables with frequency and percentage for each category.

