## **6.3 Withdrawal of Participants**

All study participants are free to discontinue the study drug and/or withdraw their consent at any point during treatment without prejudice. Participants who elect to discontinue the study drug early (receive no or one dose only) will continue with all other trial involvement unless they specify that they wish to withdraw from the study.

If a participant indicates that they wish to withdraw their consent for further participation data collected to the point of withdrawal will be retained and used. The investigator will be encouraged to ask a participant who is withdrawing which level of continued participation they agree to, if any, and to document this in the CRF. If a participant specifically requests complete withdrawal of consent, publicly available information only such as from the Birth Register may still be accessed to collect survival status. All participants will receive on-going medical care according to clinical need.

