There are no reliable data on rates of hypoglycaemia after planned CS  $\geq 35$  weeks in any published trials or cohort studies. Using New Zealand specific data for those within our cohort who are preterm, small- or large-for- gestational age (rates of hypoglycaemia 53%, 39% and 56% respectively) and for appropriately grown term babies (20% background rate of hypoglycaemia) and ADHB 2018 data for the proportion of babies born after planned CS at  $35^{+0}$  to  $39^{+6}$  weeks who fell into each of these four groups, we estimate an overall rate of hypoglycaemia of 28.2% (355/1259). To demonstrate the non-inferiority of corticosteroid use we have set a 10% non-inferiority margin (clinically relevant difference). **With an event rate of 28%, a sample size of 728 infants (364 per group) will have 90% power, with  $\alpha$  0.05, to reject inferiority (up to 38% hypoglycaemia in corticosteroid group), allowing for 3% drop out and design effect 1.02.**

As planned *a priori*, we have remained blinded to outcome data by treatment group for the C\*STEROID Feasibility Study allowing data to contribute to the main C\*STEROID Trial. Data from 88 mothers and 92 babies in the feasibility Study will contribute to the C\*STEROID Trial.

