### **10.3 Drug Administration and Assessment of Compliance**

The study drug will be administered by intramuscular injection, to the thigh, arm or buttock, by appropriately qualified clinical or research staff at the study site within seven days prior to planned CS. Two doses of study drug should be administered 24 hours apart +/- 4 hours (i.e. 20-28 hours). If the date/time of the participant's CS is brought forward and/or labour commences spontaneously before the second dose has been administered it should still be given as long as it is ≥20 hours following the first dose. If birth is planned (CS) or inevitable (spontaneous labour) and it is <20 hours since the first dose the second dose should not be given. There is no minimum timeframe between the second dose and the planned CS (or expected birth). The timing of each dose and compliance will be recorded on the CRF.

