#### **12.1.6. Neonatal blood glucose monitoring**

Neonatal blood glucose concentrations (BGC) will be measured after first feed at 1-2 hours of age and then pre-feed 3-4 hourly until 12 hours of age unless hypoglycaemia has occurred (continue monitoring until three consecutive blood glucose concentrations have been  $\geq 2.6$  mM). BGC should be measured using a glucose oxidase method, e.g. i-STAT analyser or blood gas analyser; if this is not available alternatives such as Accucheck should be used. Method of analysis will be noted with BGC recordings. If it is not possible to complete one or more of the recommended BGC this will be recorded in the CRF along with the reason why it was not carried out. Any additional clinically indicated blood glucose levels  $< 2.6$  mM recorded in the neonatal period will be collected. We will recommend that hypoglycaemia is treated following the ADHB Hypoglycaemia in the neonate guideline and the national Oral Dextrose Gel guideline. Surveillance and treatment algorithms will be supplied to sites (Appendix).

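### Non-inferiority on hypoglycaemia can be established on intention-to-treat alone, although the protocol foresees incomplete betamethasone dosing that pulls the difference towards zero

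*Protocol*

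**What the plan says.** Protocol section 16 opens with one sentence covering every endpoint: "Data will be analysed on an intention-to-treat basis". For hypoglycaemia it names the Farrington-Manning score test, which "will be used for assessing non-inferiority to compare hypoglycaemia rate between the two groups", and gives a complete decision rule, which is met when "the upper limit of the 90% confidence interval of the proportion difference between the two groups (steroid-placebo) is not greater than 10" per cent. Section 7.1 sets the margin ("we have set a 10% non-inferiority margin") and the size needed for it: "With an event rate of 28%, a sample size of 728 infants (364 per group) will have 90% power". No other analysis set is named in the protocol.

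Three sections foresee incomplete dosing. Section 6.3: "Participants who elect to discontinue the study drug early (receive no or one dose only) will continue with all other trial involvement", unless they ask to withdraw. Section 10.3: if birth is planned or inevitable less than 20 hours after the first dose, "the second dose should not be given"; at 20 hours or more it is still given. Section 11.2 lists a reaction to the first injection, birth before the second dose and maternal request as reasons to stop.

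Section 12.1.6 separately foresees missed glucose tests: "If it is not possible to complete one or more of the recommended BGC this will be recorded in the CRF", with the reason. The protocol gives no expected rate for any of these events.

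**The concern.** One analysis set serves two endpoints on which dilution acts in opposite directions. If some women in the betamethasone arm are not exposed, or only partly exposed, the observed difference moves towards zero. For respiratory distress, a superiority endpoint, that makes success harder. For hypoglycaemia, a non-inferiority endpoint, it makes success easier.

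Hypoglycaemia is the trial's measure of harm, and clinicians will read a non-inferiority result as reassurance for a baby whose mother received the full course. Under the stated rule that reassurance could rest on a difference reduced by missed doses, with no pre-specified analysis required to show whether it does.

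**Working it through.** **Inputs from the protocol.** Hypoglycaemia rate 28% (section 7.1); margin 10 points (sections 7.1 and 16); upper limit of a 90% interval, so one-sided 5% (section 16); 364 infants per group for this endpoint and 1274 per group overall; 3% drop-out and design effect 1.02 (section 7.1).

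**Reproducing the plan's figure.** n per group = (1.645 + 1.282)² × 2 × 0.28 × 0.72 / 0.10² = 346 after rounding up. Inflated: 346 × 1.02 / 0.97 = 363.8, so 364 per group and 728 in total, as stated. At one-sided 2.5% the total would be 892, so the plan used one-sided 5%.

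**Effective size at analysis.** The respiratory endpoint drives recruitment: 1274 × 0.97 / 1.02 ≈ 1212 effective infants per arm. The size computed for hypoglycaemia alone gives 364 × 0.97 / 1.02 ≈ 346.

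**Assumptions not in the protocol.** A share f of the betamethasone arm is unexposed and has no drug effect. The true difference under full treatment is D = 10 points (38% v 28%).

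**Formulas.** Intention-to-treat difference d = D × (1 − f). Chance of declaring non-inferiority ≈ Φ((0.10 − d)/SE − 1.645), with SE = √{[0.28 × 0.72 + (0.28 + d)(0.72 − d)]/n}.

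For f = 10% and n = 1212: d = 0.09; SE = √[(0.2016 + 0.2331)/1212] = 0.0189; 0.01/0.0189 − 1.645 = −1.12; Φ = 13%.

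The table uses the Farrington-Manning version of this approximation, which gives nearly the same values.

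| Unexposed f | Intention-to-treat difference (points) | Chance, n = 1212 | Chance, n = 346 |
|---|---|---|---|
| 0% | 10.0 | 5% | 5% |
| 5% | 9.5 | 8% | 7% |
| 10% | 9.0 | 13% | 9% |
| 15% | 8.5 | 20% | 11% |
| 20% | 8.0 | 28% | 14% |
| 30% | 7.0 | 48% | 21% |

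The larger trial is affected more, because its interval is narrower around the diluted value.

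If D is 12 points and n = 1212, the chance is 0.4%, 0.9%, 1.9%, 7.6% and 21% at f = 0, 5, 10, 20 and 30%. Among true differences at or beyond the margin, exactly 10 points is therefore the worst case. For scale, the largest late-preterm trial cited in section 2.1 reported 22.8% v 14.2%, a difference of 8.6 points, though section 2.1 notes that glucose was not measured systematically there.

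**Missed glucose tests, kept separate.** If incomplete monitoring lowers detection equally in both arms, at 90% sensitivity 38% v 28% becomes 34.2% v 25.2%, a difference of 9.0 points, and the chance is 14% (n = 1212). If detection differs between arms, the shift can go either way.

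**Power of an added per-protocol analysis.** With 28% in both arms, one-sided 5% and design effect 1.02, starting from 1274 per arm, power is above 99.9% when 10% or 20% are excluded and 99.9% when 30% are.

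**The case against.** The strongest objection concerns the target. The protocol sets its margin on the difference between randomised groups. On that quantity the error rate is the nominal 5%, and a true between-group difference of 9 points lies inside the margin, so declaring non-inferiority there is correct. Withholding the second dose within 20 hours is also the protocol's own rule and part of the policy being tested. This stands. A reader might infer that intention-to-treat is the wrong primary set, or that the trial's type I error is inflated; the documents support neither. The percentages above are errors only against the effect in fully treated women.

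A reader might also infer that every missed dose or missed test dilutes the difference. That is not so:

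- A missed placebo injection changes nothing, and section 11.1 bars further antenatal corticosteroids, so the protocol offers no planned crossover.
- Missed glucose tests are an ascertainment problem, not a consequence of intention-to-treat. The endpoint is any low value before primary discharge, and section 12.1.6 also collects clinically indicated low values, so an incomplete series need not mean a missed event.

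Dilution also lowers the chance of success on respiratory distress, and the trial needs both endpoints. That makes the joint claim harder but does not protect the hypoglycaemia conclusion itself.

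Finally, a supportive per-protocol set is common SAP content, and the SAP is not at hand. That limits what can be said about omission. It does not alter the fact that section 16 states when non-inferiority is established, and that this statement needs intention-to-treat alone.

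**Conclusion.** The point holds in a limited form. The success rule for the harm endpoint leans towards the claim when betamethasone dosing is incomplete, and the protocol foresees such dosing without requiring a second analysis to agree.

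The size depends on assumptions. With a true full-treatment difference exactly at the margin and about 1212 effective infants per arm, the chance of declaring non-inferiority is at most about 8%, 13% and 28% at 5%, 10% and 20% unexposed. These are upper bounds, since a single dose is counted as having no effect. At 5% unexposed the excess over 5% is small; at 10 to 20% it matters. The protocol gives no rate, so it cannot be said which applies, nor that harm will be missed. Intention-to-treat remains valid for the effect of the offered policy.

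**What to change.** Keep intention-to-treat as the primary set for both endpoints. In section 16, for hypoglycaemia only, pre-specify a per-protocol analysis defined by study-drug dosing as scheduled, and state before unblinding how women whose second dose was withheld under section 10.3 are classified. Require the upper limit in this set to support the same conclusion before non-inferiority is claimed.

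Do not define the set by completeness of the glucose series. Completeness arises after randomisation and is tied to outcome, since section 12.1.6 prolongs monitoring when hypoglycaemia occurs. Selecting on it could bias the comparison in an unknown direction. Handle incomplete monitoring separately, with a pre-specified missing-measurement sensitivity analysis.

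The cost is a sentence or two in section 16 and additional tables. No extra infants are needed, and dose timing, compliance and missed tests are already recorded in the CRF. The downside is a slightly stricter claim and a supportive set that randomisation does not protect, which is why it sits beside intention-to-treat and does not replace it. If the SAP already contains these analyses, align section 16 with it.

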## **7. STUDY NUMBERS & POWER CALCULATION**

### **7.1 C\*STEROID Trial**

We hypothesise that corticosteroid use will reduce neonatal respiratory distress without increasing neonatal hypoglycaemia and therefore have selected co-primary outcomes of a superiority endpoint for benefit and non-inferiority endpoint for harm. The efficacy of corticosteroids is based on the success of both co-primary endpoints; therefore, no multiplicity adjustment is necessary.

Published literature only provides surrogate estimates for the incidence of respiratory distress requiring  $\geq 60$  minutes of support which varies by gestation and mode of birth. The rate of mask

and/or mechanical ventilation use is 4.4% (21/475) after planned CS  $\geq 37^{+0}$  weeks but 16.3% (258/1580) for all births at  $34^{+0}$  to  $36^{+6}$  weeks. To best estimate the incidence of this outcome we have used ADHB 2018 data for planned CS at  $35^{+0}$  to  $39^{+6}$  weeks; from a total of 1259 planned CS, 63 infants required  $>60$  minutes respiratory support (5.0%).

Using a conservative relative risk reduction of 0.5 and 5.0% event rate, **a sample size of 2424 infants (1212 per group) will have 90% power, with  $\alpha$  0.05, to detect a reduction from 5.0% to 2.5%. We will recruit 2548 infants (1274 per group) to allow for 3% drop out and design effect 1.02** (clustering of babies within mothers estimated 1.02 babies per mother with ICC of 0.8, based on the incidence of multiples at this gestation in the ADHB dataset).

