## **9. RANDOMISATION**

Eligible women who have provided written, informed consent to participate will be enrolled by clinicians and research staff using a web-based randomisation service operating at the Clinical Data Research Hub Research Hub (CDRH) hosted by the Liggins Institute, The University of Auckland.

Randomisation will be stratified for;

1. Gestational age at planned caesarean section 35+0-36+6, 37+0-38+6, 39+0-39+9 weeks
2. Recruiting site
3. Singleton or twin pregnancy

Women will be randomised in a 1:1 ratio to betamethasone:placebo.

The randomisation process will assign each participant with a unique study ID number. This study ID number will be required when allocating study drug treatment pack and for recording data on the CRF. The randomisation service provides 24 hour access, 7 days per week. If a woman is found not to be eligible for the trial when her details are entered into the randomisation program the program will return a screen failure notification.

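### The hypoglycaemia non-inferiority test ignores the twin clustering that the protocol's own sample size allows for; the net effect is small and the correction is free

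*Protocol*

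**What the plan says.** Women are randomised and infants are analysed. Twin pregnancies are eligible (section 6.1). Allocation is stratified by gestational age at planned caesarean, recruiting site, and singleton or twin pregnancy (section 9).

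Section 16 treats the two co-primary outcomes differently:

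- Respiratory distress: "To account for the correlation of twins, we will use marginal logistic regression model via generalised estimating equations to assess the treatment effect", and this "on respiratory distress adjusting for randomisation variables and other confounders which may influence the outcome of interest".
- Hypoglycaemia: the Farrington-Manning score test "will be used for assessing non-inferiority to compare hypoglycaemia rate between the two groups". The decision rule follows: "Non-inferiority is established if the upper limit of the 90% confidence interval of the proportion difference between the two groups" (steroid minus placebo) does not exceed 10%. No cluster or stratum term is given.

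Section 7.1 does recognise clustering for hypoglycaemia. Its 728 infants include 3% drop-out and a design effect of 1.02. The respiratory paragraph of the same section explains where that factor comes from: "clustering of babies within mothers estimated 1.02 babies per mother with ICC of 0.8". Section 7.1 also says of the feasibility study: "Data from 88 mothers and 92 babies in the feasibility Study will contribute".

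**The concern.** The Farrington-Manning test compares two independent binomial samples. Twins share a mother, an allocation and much of their risk, so they are not independent. A test that ignores this gives an interval that is too narrow, which on a harm endpoint is the unsafe direction. The protocol allowed for this when it sized the endpoint, then named a test that does not.

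The same test also ignores gestation, which is a stratification factor. On section 7.1's planning figures gestation is prognostic: 53% hypoglycaemia in preterm babies against 28.2% overall. An unstratified interval after stratified randomisation is too wide, which is conservative and costs precision.

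Success of the trial needs both co-primary outcomes (sections 7.1 and 15.1), so the harm test should hold its stated error rate.

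**Working it through.** **Inputs.** From section 7.1: 28% hypoglycaemia in both arms, margin 10 points, 90% power, alpha 0.05, drop-out 3%, design effect 1.02, 1.02 babies per mother, ICC 0.8, 53% hypoglycaemia in preterm babies, 1274 infants per arm recruited, feasibility study 88 mothers and 92 babies. From section 16: 90% interval, so one-sided 5%. Assumed, because the protocol does not give them: four twin pairs in the feasibility study, and 5-15% of infants in the 35-36 week stratum.

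**1. The plan's own figure.** n per arm = 2 × 0.28 × 0.72 × (1.645 + 1.282)² / 0.10² = 345.3, rounded up to 346. Then 346 × 1.02 / 0.97 = 363.8, giving 364 per arm and 728 in total. This reproduces the protocol exactly, with the design effect included and alpha one-sided.

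**2. Design effect for twins.** The stated 1.02 matches 1 + (1.02 − 1) × 0.8 = 1.016. With unequal cluster sizes the infant-weighted form is more exact: 1 + (Σm²/Σm − 1) × 0.8.

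- 2% twin pregnancies, per 100 mothers: Σm² = 98 + 2 × 4 = 106 and Σm = 102, so the design effect is 1 + 0.0392 × 0.8 = 1.031.
- Feasibility ratio: 84 singletons and four pairs, so Σm² = 84 + 16 = 100 and Σm = 92. The design effect is 1 + 0.0870 × 0.8 = 1.070.

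**3. Twins alone.** Actual one-sided error = 1 − Φ(1.645 / √DE).

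| Design effect | Error by formula | Error by simulation of the test, 38% vs 28%, 1274 per arm |
|---|---|---|
| 1 (no twins) | 5.00% | 4.99% |
| 1.031 | 5.26% | 5.26% |
| 1.070 | 5.59% | 5.55% |

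**4. Strata alone.** Let s be the preterm share, at 53%, with 28% overall. The remaining infants then have rate (0.28 − 0.53s)/(1 − s). The between-stratum variance is B = s(1 − s)(0.53 − rest)². At the boundary, with 10 points added in each stratum of the steroid arm, the factor is 1 − 2B/(0.28 × 0.72 + 0.38 × 0.62).

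- s = 5%: rest 26.7%, B = 0.0033, factor 0.985.
- s = 15%: rest 23.6%, B = 0.0110, factor 0.950.

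Both factors are below 1, so omitting the strata is conservative.

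**5. Both together.** Multiply the two factors and apply the formula in step 3 (normal approximation).

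| Preterm share (assumed) | Design effect 1.031 | Design effect 1.070 |
|---|---|---|
| 5% | 1.016, error 5.1% | 1.053, error 5.4-5.5% |
| 15% | 0.979, error 4.8% | 1.016, error 5.1% |

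**6. Effect on the decision limit.** The half-width of the 90% interval at 28% in both arms with 1274 per arm is 1.645 × √(2 × 0.28 × 0.72 × DE / 1274). This is 2.93 points with infants independent, 2.97 at 1.031 and 3.03 at 1.070. The shift is 0.04 to 0.10 points. Power stays above 99.9% throughout.

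**The case against.** The strongest reply is that nothing of consequence follows. The endpoint needs 728 infants and the trial recruits 2548. The upper limit moves by at most about 0.1 point against a 10-point margin, so the conclusion could change only for a result lying almost on the margin. That stands, and it is why the point is minor.

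A reader might go further and infer that the test is shown to be off its nominal level, or that it will declare non-inferiority falsely too often. The documents do not support this. The two omissions pull in opposite directions. At the protocol's planned cluster size the combined error is 4.8-5.1%, which is nominal for practical purposes. Error above 5% across the whole assumed range appears only at the feasibility ratio, and that rests on four extra babies among 88 mothers. If these are four twin pairs, the exact 95% interval for the twin share is about 1.3% to 11%. The ICC of 0.8 is stated in the respiratory paragraph; none is given specifically for hypoglycaemia, and a lower value would shrink the twin effect.

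It is also fair that the contrast of 53% in preterm with 20% in appropriately grown term babies overstates what gestation adds. Small and large babies have planning rates of 39% and 56%, and size is not a stratification factor. The working therefore sets preterm babies against the average of all the rest. Omitting the strata cannot by itself produce false non-inferiority, so that part concerns precision and consistency only.

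The reply that this is a matter for the SAP does not hold. The protocol is not silent: it names the test for a co-primary outcome and, on clustering, that test conflicts with the protocol's own sample size.

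**Conclusion.** The inconsistency is real. Section 16 accounts for twins and the randomisation variables for one co-primary outcome and not for the other, while section 7.1 applies a clustering factor to both. Its size is small: a one-sided error of about 4.8-5.5% against a nominal 5%, in a direction that depends on the twin share and the gestation mix. These figures rest on an ICC of 0.8, a twin share between 2% of pregnancies and the feasibility ratio, an assumed 5-15% preterm share at 53%, and a normal approximation that multiplies the two factors. That they may partly cancel is a matter of case mix and no reason to prefer the named test. This is a minor point, worth acting on because the better analysis uses data and a model that the trial already has.

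**What to change.** In section 16, make the primary hypoglycaemia analysis an estimate of the steroid-minus-placebo risk difference by GEE, clustered on mother with robust standard errors and adjusted for gestation stratum and plurality. Use either a binomial model with identity link or a risk difference standardised from a logistic GEE of the kind already planned for respiratory distress. Compare the upper limit of its 90% interval with the existing 10% margin. Keep the Farrington-Manning test as a sensitivity analysis. The sample size need not change.

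Cost: a few sentences of protocol wording, carried into the SAP, and a few lines of code. No new data are needed. The change should be made before unblinding.

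### Non-inferiority on hypoglycaemia is judged at one-sided 5%, a looser and unexplained level than the benefit endpoint; the 95% limit would need no extra infants

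*Protocol*

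**What the plan says.** Section 16 first sets a general standard: "Two sided-p-values less than 0.05 will be used to determine statistical significance", and "confidence intervals will be reported at a two-sided 95% level". It then names the Farrington-Manning score test, which "will be used for assessing non-inferiority to compare hypoglycaemia rate between the two groups", and gives that test its own decision rule: "Non-inferiority is established if the upper limit of the 90% confidence interval of the proportion difference between the two groups" (steroid minus placebo) is no greater than 10%. No reason is given for moving from 95% to 90%.

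Section 7.1 explains the margin: "we have set a 10% non-inferiority margin (clinically relevant difference"). It sizes this endpoint as follows: "With an event rate of 28%, a sample size of 728 infants (364 per group) will have 90% power". Alpha is given as 0.05, with allowance for 3% drop-out and a design effect of 1.02. The respiratory calculation in the same section also gives alpha as 0.05 and leads to the recruitment target of 2548 infants (1274 per group). Neither statement says whether alpha is one-sided or two-sided.

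Sections 7.1 and 15.1 both require the two co-primary outcomes to succeed together: "The efficacy of corticosteroids is based on the success of both co-primary endpoints; therefore, no multiplicity adjustment is necessary".

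**The concern.** The trial is meant to show benefit without harm, and the harm half of that claim has the weaker standard of proof. A 90% interval read at its upper end allows a 5% chance of declaring non-inferiority when the true excess is exactly 10 points. A two-sided 95% interval allows 2.5%, which is the directional error applied to the benefit endpoint.

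Requiring both endpoints to succeed removes the need to split alpha. It does not justify a looser level for one of them, because the worst-case error of a both-must-pass claim is that of its weaker test.

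A reader of section 7.1 cannot see the difference, since the same alpha of 0.05 stands for two different directional error rates.

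**Working it through.** **Inputs.** From section 7.1: placebo hypoglycaemia rate 28%, margin 10 points, 90% power, 3% drop-out, design effect 1.02, respiratory rates 5.0% and 2.5%, and 1274 infants per group recruited. From section 16: the 90% interval rule and the Farrington-Manning test.

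**Step 1: which alpha gives 364 per group?** With equal true rates, n per arm = (z₁₋α + z₀.₉₀)² × 2 × 0.28 × 0.72 / 0.10².

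- One-sided 0.05: (1.645 + 1.282)² × 0.4032 / 0.01 = 345.3. Then 345.3 × 1.02 / 0.97 = 363.1, or 363.8 if 345.3 is first rounded up to 346. Both round up to the stated 364.
- One-sided 0.025: (1.960 + 1.282)² × 0.4032 / 0.01 = 423.7. Then 423.7 × 1.02 / 0.97 = 445.5, so 446 per group or 892 in total. This does not match.

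The Farrington-Manning formula gives the same whole numbers before inflation, 346 and 424.

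**Step 2: which alpha gives 1212 per group?** The pooled formula for 5.0% against 2.5% has mean rate 0.0375.

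- Two-sided 0.05: [1.960 × √(2 × 0.0375 × 0.9625) + 1.282 × √(0.05 × 0.95 + 0.025 × 0.975)]² / 0.025² = 1211.5, so 1212 as stated.
- One-sided 0.05 (1.645 in place of 1.960): 987.2, so 988. This does not match.

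The same alpha of 0.05 is therefore two-sided for benefit and one-sided for harm.

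**Step 3: effective size.** 1274 × 0.97 / 1.02 = 1211.5 infants per arm.

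**Step 4: error at the margin.** With true rates of 28% and 38%, one million simulated trials of 1211 per arm, using unpooled limits, declared non-inferiority in 5.02% with the 90% interval and 2.50% with the 95% interval.

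**Step 5: largest observed excess that passes.** With an observed placebo rate of 28% and a steroid rate of 36.5% in the standard error, SE = √[(0.28 × 0.72 + 0.365 × 0.635) / 1211.5] = 0.0189.

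- 90% interval: 0.10 − 1.645 × 0.0189 = 0.069.
- 95% interval: 0.10 − 1.960 × 0.0189 = 0.063.

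**Step 6: chance of passing, by true excess** (Farrington-Manning, 1211.5 per arm, placebo rate 28%).

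| True excess | One-sided 5% | One-sided 2.5% |
|---|---|---|
| 0 points | 99.99% | 99.98% |
| +2 | 99.7% | 99.1% |
| +3 | 98.4% | 96.6% |
| +4 | 94.3% | 89.8% |
| +5 | 85.0% | 76.5% |

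If only 728 infants were recruited (about 346 effective per arm), power at one-sided 2.5% would be 83.4%. That shortfall does not arise, because 2548 are recruited.

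**The case against.** The best defence is that nothing here is inconsistent. The sentence on 95% intervals is a general reporting rule, and the sentence after it is a specific rule for a one-directional test. The specific rule names the test, the direction and the limit, and the sample size was computed at the same level. No passage commits the trial to one-sided 2.5% for non-inferiority. All of this stands. A reader might infer that the 90% interval contradicts the 95% statement, or that 728 is a miscalculation; the documents support neither.

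A reader might also infer that the looser level buys nothing. That is true only under the planning assumption of equal rates. Section 2.1 reports 22.8% against 14.2% hypoglycaemia in the large late-preterm trial and calls a causal effect physiologically plausible, so a real increase cannot be set aside. For a true excess of 4 or 5 points, which is inside the protocol's own margin, the stricter rule lowers the chance of passing by 4.5 and 8.5 points.

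Finally, a reader might say that the whole benefit-without-harm claim carries a 5% error. That is a worst-case bound. Success also needs the respiratory endpoint; at its planned 90% power, and assuming independence, the joint rate at the margin is 0.90 × 5% = 4.5%, against 0.90 × 2.5% = 2.25% under the stricter rule. The ratio is still two, but the decision threshold moves by only 0.6 points.

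The defence does not supply a reason for the looser level on the harm endpoint, and it does not account for the missing sidedness in section 7.1.

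**Conclusion.** The point holds as a moderate one: a lenient, unexplained choice on the harm co-primary that section 7.1 obscures. It is neither an arithmetic error nor a flaw that invalidates the design. The stricter level halves the error at the margin without more infants and, on the planning assumption of no true increase, with a power loss of about 0.01 percentage points. If there is a true increase inside the margin, the trial becomes less likely to pass. For a test meant to rule out harm that is a reasonable trade, but it is a cost and should be acknowledged.

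The figures assume a 28% placebo rate, 3% drop-out and a design effect of 1.02, all taken from section 7.1.

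**What to change.** - In section 16, declare non-inferiority when the upper limit of the two-sided 95% confidence interval for steroid minus placebo (one-sided alpha 0.025) does not exceed 10 percentage points.
- In section 7.1, state that alpha is two-sided 0.05 for respiratory distress and one-sided 0.025 for hypoglycaemia. To match, restate the hypoglycaemia requirement as about 892 infants (446 per group), still far below 2548.
- Make the change before unblinding, and carry the same rule into the SAP if there is one.

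If the sponsor prefers to keep one-sided 5%, the least that is needed is a stated reason, the sidedness of each alpha in section 7.1, and a commitment to report the 95% limit against the margin as well.

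The cost is a few sentences of wording and no recruitment. The lower chance of passing under a real increase of 4 to 5 points should be disclosed with the change.
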